## 9.3.5. Treatment Comparisons

#### 9.3.5.1. Primary Comparison of Interest

The primary comparison of interest at year 2 (Month 24 visit) is the combination therapy versus 0.2mg tamsulosin in terms of change from baseline IPSS. The primary population of interest will be the ITT population and the primary comparison will be made using LOCF data.

If the Month 24 IPSS change from baseline two-sided p-value is  $\leq 0.05$  and the treatment difference supports combination superiority, then conclude that combination is superior to 0.2mg tamsulosin.

If the IPSS primary efficacy endpoint is statistically significant and treatment difference supports combination superiority at Month 24, as defined above, then statistical testing and interpretation of earlier visit timepoints (Month 21, Month 18, Month 15, Month 12, Month 9, Month 6, Month 3 – in this order) will occur in a step-down manner [producing a closed test procedure] at the 0.05 level of significance. Multiplicity control for secondary endpoints will be defined in the RAP.

## 9.3.5.2. Other Comparisons of Interest

Secondary endpoint treatment comparisons of interest are included in this section

## Secondary Efficacy Endpoints:

- Prostate volume % change from baseline
- IPSS improvement of ≥2 points and ≥3 points and, separately, ≥25% improvement from baseline
- Qmax change from baseline
- Proportion of subjects with Qmax improvement of ≥3ml/sec and, separately, ≥30% improvement from baseline
- Time to event/ proportion of subjects with AUR or BPH related prostatic surgery
- Time to event/proportion of subjects with AUR
- Time to event/proportion of subjects undergoing BPH related prostatic surgery

#### Health Outcomes Endpoints:

- BPH Impact Index (BII) change from baseline
- BPH-related Health Status (Q8 of IPSS) change from baseline
- Problem Assessment Scale of the Sexual Function Inventory (PAS- SFI) change from baseline

## 9.3.6. Interim Analysis

No interim efficacy analyses are planned for this study.

## 9.3.7. Key Elements of Analysis Plan

Data will be listed and summarized according to the GSK reporting standards, where applicable. Complete details will be documented in the RAP. Any deviations from, or additions to, the original analysis plan described in this protocol will be documented in the RAP and final study report.

As it is anticipated that accrual will be spread thinly across centers and summaries of data by center would be unlikely to be informative, data from all participating centers will be pooled prior to analysis. Investigative centers will be pooled a priori into clusters based on geographic location; these clusters may be used in analyses to adjust for site effects. Clusters will be defined once all investigative sites have been identified and randomisation has been completed.

All data up to the time of study completion/withdrawal from study will be included in the analysis, regardless of duration of treatment.

Analyses will be performed as appropriate using the LOCF along with the At Visit approach or the observed-cases approach and which will be assigned in subsequent sections. Missing individual responses for the IPSS questionnaire will be imputed when at least four of the seven questions are answered (non-missing). Missing individual responses for the BII questionnaire will be imputed when at least two of the four questions are answered (non-missing). For the imputation, the average of the non-missing responses will be calculated and rounded to the nearest integer. This average score will be imputed for the original missing response(s). If at least 20% of the subjects have at least one imputed score for either IPSS or BII then that questionnaire's statistical analyses will be repeated based on non-imputed scores.

For purposes of data analyses, the baseline value of a particular type of assessment for a given subject will be defined as the last assessment prior to the start of randomized treatment. Change from baseline for each subject will be computed as post-baseline value minus baseline value. Endpoints will be log-transformed where this will improve the assumptions underlying the analyses. Endpoints with log-transformations performed within the analysis model include prostate volume.

Demographic and baseline characteristics will be summarized.

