#### **BPH Impact Index**

The BPH Impact Index (BII) is the sum of four questions with a total score range of 0 to 13. Individual questionnaire missing responses will be imputed, if applicable, as defined in Section 9.3.7. Total BII, change from baseline BII, and percentage change from baseline BII will be summarized by treatment group using both the LOCF and At Visit approaches at each scheduled post-baseline assessment. Change in baseline BII will be compared at each scheduled post-baseline assessment using a general linear model with effects for treatment, cluster, and baseline BII.

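### The item-imputation rule can return a BII total above the scale maximum of 13, and its rounding step adds avoidable error to single IPSS totals

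*Protocol*

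**What the plan says.** Protocol Section 9.3.7 fixes the rule. For IPSS, "Missing individual responses for the IPSS questionnaire will be imputed when at least four of the seven questions are answered"; for BII the threshold is two of four. Up to three IPSS items or two BII items can therefore be filled in. The value used is the same for both instruments: "the average of the non-missing responses will be calculated and rounded to the nearest integer", and it goes into each missing item. The section gives no rule for ties, no cap at an item's maximum and no adjustment for items of different length.

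The primary analysis in Section 9.3.7.1 refers back to this rule for IPSS, and the BPH Impact Index paragraph of Section 9.3.7.3 does so for BII. That paragraph says the BII "is the sum of four questions with a total score range of 0 to 13".

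One safeguard is stated: "If at least 20% of the subjects have at least one imputed score for either IPSS or BII", that questionnaire's analyses are repeated on non-imputed scores.

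**The concern.** Filling a missing item with the mean of the answered items presumes that the items share a scale. The protocol's own description of the BII shows that they do not, so the rule can assign an answer that the item does not offer and a total that the instrument cannot produce.

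For IPSS the issue is smaller. Rounding the mean and then using it up to three times multiplies the rounding error by the number of missing items, with nothing gained. IPSS feeds the primary endpoint and the responder endpoints of at least 2 and at least 3 points. Because LOCF is the primary approach, one affected post-baseline score can be carried to Month 24, and an affected baseline enters every change score for that subject.

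**Working it through.** **BII: inputs.** Four questions, total 0 to 13 (Section 9.3.7.3); at least two answered (Section 9.3.7). The item maxima are not in the public protocol because the questionnaire pages are withheld for copyright. I assume integer items starting at 0. Maxima of 3, 3, 3 and 4 reproduce the stated range (3 + 3 + 3 + 4 = 13), but they are an assumption.

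**BII: what follows without knowing the maxima.**
- A common maximum would be 13 / 4 = 3.25, which is not an integer, so the maxima differ.
- The two largest maxima sum to at least half of 13, that is 6.5, hence at least 7.
- Top answers on those two items, with the other two missing, give a mean of at least 7 / 2 = 3.5. This becomes at least 4 under half-up or half-to-even rounding.
- The total is then at least 7 + 2 × 4 = 15, above 13.

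**BII: with maxima 3, 3, 3, 4.**
- Answers 4 and 3, two items missing: mean 3.5, rounded to 4, total 4 + 3 + 4 + 4 = 15. Two items that stop at 3 are scored 4.
- One item missing: 3 × (4 × 4 × 5) + 4 × 4 × 4 = 304 answer patterns, none above 13. Two missing: 3 × (4 × 4) + 3 × (4 × 5) = 108 patterns, 3 above 13, all equal to 15. So 3 of 412 patterns overflow. These are counts of possible patterns, not probabilities.
- Half-down rounding turns 3.5 into 3, giving a total of 13 and no overflow.
- Without rounding: 7 + 2 × 3.5 = 14, still out of range.

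**IPSS: formula.** With k of 7 items answered, the error in the total from rounding is (7 − k) × (rounded mean − mean). The bounds do not depend on the item range.

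| Answered | Missing | Largest rounding error per item | Largest error in total |
|---|---|---|---|
| 4 | 3 | 0.5 | 3 × 0.5 = 1.5 |
| 5 | 2 | 0.4 | 2 × 0.4 = 0.8 |
| 6 | 1 | 0.5 | 1 × 0.5 = 0.5 |

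**IPSS: responder example.** Take a complete baseline of 20 and a follow-up with four answered items summing to 10, mean 2.5.
- Unrounded: 10 + 3 × 2.5 = 17.5, improvement 2.5.
- Half-up: 10 + 3 × 3 = 19, improvement 1.
- Half-to-even: 10 + 3 × 2 = 16, improvement 4.

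The same answers fail the 2-point threshold, meet only that one, or meet both the 2- and 3-point thresholds, depending on a convention that the protocol does not state.

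**IPSS: direction on average.** Assuming items scored 0 to 5 and all patterns equally likely, the mean error with three items missing is +0.38 under half-up, −0.007 under half-to-even and −0.38 under half-down.

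**Safeguard.** 20% of 586 is 117.2, so up to 117 randomized subjects could have an imputed score without triggering the repeat.

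**The case against.** The strongest reply is that the overflow is a corner case. It needs two of four items missing and top answers on both of the others, and under half-down rounding it disappears for maxima of 3, 3, 3 and 4. Section 7.5.2 asks subjects to complete the questionnaires fully, and Section 9.3.7 leaves complete details to the reporting and analysis plan, where a tie convention and a cap could be set. Apart from the overflow, person-mean filling and range scaling are both assumptions about answers that nobody has, and rounding keeps an integer score on an integer instrument.

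Much of this stands. It limits the point to few subjects, and outside the overflow cases the choice between the two methods is partly preference: averaged over equally likely two-missing patterns with the assumed maxima, the BII result differs from range scaling by +0.56, +0.06 or −0.44 under half-up, half-to-even and half-down. It does not remove the defect. The protocol states the rule in full rather than deferring it, and the rule can break the range that the protocol itself gives. The 20% repeat does not help: below the trigger nothing happens, and above it the repeat uses non-imputed scores and leaves the out-of-range totals in the main analysis.

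A reader might infer a systematic upward bias in the scores. The document does not support that, because the sign of the average depends on a tie rule that it does not state.

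**Conclusion.** The point holds as a minor scoring defect. That a BII total above 13 can arise follows from the protocol's own description under half-up or half-to-even rounding, given integer items starting at 0. The figure of 15 as the ceiling also rests on the assumed maxima. The IPSS bounds of 1.5, 0.8 and 0.5 points are exact worst cases for one subject at one assessment, of either sign.

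A reader might set 1.5 against the planned IPSS difference of 1.8 and conclude that the primary comparison is at risk. That does not follow: 1.8 is a difference between group means, and the same rule applies in both arms, so most of the error should cancel. Even in an extreme case, with 20% of one arm carrying the full 1.5 points and none in the other, the mean difference would move by 0.2 × 1.5 = 0.3. The practical consequence is confined to occasional impossible BII values and occasional changes in an individual's responder status.

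**What to change.** In Section 9.3.7, drop the rounding and score the two instruments separately:
- IPSS, at least four items answered: total = mean of the answered items × 7.
- BII, at least two items answered: total = (sum of the answered items / sum of those items' maxima) × 13. Answers of 4 and 3 on the assumed maxima then give 7 / 7 × 13 = 13.

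The minimum change for BII is to cap each imputed item at its own maximum, which in the same example gives 4 + 3 + 3 + 3 = 13. Removing the rounding without a cap or scaling is not enough, since 14 remains reachable. If rounding is kept, state the tie rule.

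The cost is two sentences of text and the matching score derivation. The only downside is non-integer totals for questionnaires with imputed items.

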## 9.3.7.1. Efficacy Analyses

#### **Primary Analysis**

The primary efficacy parameter after two years of study treatment is change from baseline IPSS. Symptom improvement is measured using the IPSS and evaluated using change from baseline.

Total IPSS, change from baseline IPSS, and percentage change from baseline IPSS will be summarized by treatment group using both the LOCF and At Visit approaches at each scheduled post-baseline assessment. Change in baseline IPSS will be compared at each scheduled post-baseline assessment for combination therapy versus 0.2mg tamsulosin using a general linear model with effects for treatment, cluster, and baseline IPSS at alpha=0.05.

CONFIDENTIAL

Missing individual responses for the IPSS questionnaire will be imputed as defined in Section 9.3.7.

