#### 7.2.2.1. International Prostate Symptom Score (IPSS)

The IPSS is a 7 item instrument (essentially the same as the American Urological Association Symptom Index, AUA-SI) designed to quantify urinary symptoms but with an additional, independent eighth question on quality of life (See Appendix 5). The IPSS will be administered at Pre-screening (Visit 1a), at Baseline (Visit 2) and at every 13 week clinic visit thereafter during the study treatment period. At Pre-screening (Visit 1a), subjects with IPSS <12 points (based on the first 7 questions) should be excluded from the study. Also, subjects must be instructed to abstain from using any alpha adrenergic agonist, cholinergic or anticholinergic agents including anti-histamines or decongestants within 48 hours prior to conducting each IPSS. In addition subjects must also abstain from taking selective beta 3-adrenoceptor agonist (mirabegron) for over-active bladder syndrome two weeks prior to each IPSS. If the subject did not adhere to these guidelines, study procedures should not be performed and the visit should be rescheduled.

For details of the IPSS assessment see Section 7.5.1.

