#### 7.2.2.3. Urinary Flow Measurement

Measurements of urinary flow will be conducted using a Uroflow Meter (details will be provided in the study procedures manual) at Screening Visit 1a/b, Baseline (Visit 2) and every scheduled 26 week clinic visit post-randomisation thereafter during the treatment period.

The following assessments will be collected:

• peak (maximum) flow  $(Q_{max})$  at a voided volume  $\ge 125$  ml at all visits

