#### **Secondary Analyses**

The year 2 secondary efficacy endpoints include: Qmax; prostate volume; IPSS improvement of  $\geq 2$  points,  $\geq 3$  points and, separately,  $\geq 25\%$  improvement from baseline; and Qmax improvement of  $\geq 3$ ml/sec and, separately,  $\geq 30\%$  improvement from baseline. Time to AUR or BPH-related surgical intervention is also a secondary efficacy endpoint.

The following describes the year 2 secondary efficacy endpoints and associated analyses. All treatment comparisons referenced are in terms of the combination therapy versus 0.2 mg tamsulosin.

 Prostate volume, change from baseline prostate volume, and percentage change from baseline prostate volume will be summarized by treatment group using both the LOCF and At Visit approaches at each scheduled post-baseline assessment.
 Percentage change from baseline prostate volume will be compared at each scheduled post-baseline assessment using the following general linear model:

log(post-baseline prostate volume/baseline prostate volume) = log(baseline prostate volume) + treatment + cluster

- Symptom improvement is measured using the IPSS and also evaluated using a categorical change from baseline improvement of ≥2 points and ≥3 points and, separately, ≥25% improvement from baseline. Treatment comparisons will utilise a Mantel-Haenszel test controlling for cluster at alpha=0.05.
- Maximum urinary flow (Qmax), change from baseline Qmax, and percentage change from baseline Qmax will be summarized by treatment group using both the LOCF and At Visit approaches at each scheduled post-baseline assessment. Change from baseline Qmax will be compared at each scheduled post-baseline assessment using a general linear model with effects for treatment, cluster, and baseline Qmax.
- Qmax improvement of ≥3mL/sec and, separately, ≥30% improvement from baseline will be computed by treatment group. Treatment comparisons will utilise a Mantel-Haenszel test controlling for cluster at alpha=0.05.
- Time to first AUR or BPH-related surgical intervention will be defined as the number of days from date of first dose of randomized study drug to date of the first event (earliest occurring of either AUR or BPH-related surgery) for each subject. Censoring will occur at the earliest of the following dates as applicable: the date of prostatectomy, the date of last contact for AUR and surgical intervention assessment,

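### The primary IPSS model adjusts only for the Visit 2 score, although every eligible man also has a Visit 1a score: a small missed gain in precision, not an error

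*Protocol*

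**What the plan says.** The primary comparison in section 9.3.7.1 is made "using a general linear model with effects for treatment, cluster, and baseline IPSS at alpha=0.05". Section 9.3.7 settles which value that is: "the baseline value of a particular type of assessment for a given subject will be defined as the last assessment prior to the start" of randomised treatment. For IPSS this is Visit 2.

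Section 7.2.2.1 schedules an earlier score: "The IPSS will be administered at Pre-screening (Visit 1a), at Baseline (Visit 2) and at every 13 week clinic visit thereafter". The Visit 1a score is the entry test, because at that visit "subjects with IPSS <12 points (based on the first 7 questions) should be excluded from the study".

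Other measures follow the same pattern:
- **BHS and BII:** Visits 1a and 2 (Table 1, section 7.5.1).
- **PAS-SFI:** Visits 1b and 2 (section 7.5.1).
- **Qmax:** measured "at Screening Visit 1a/b, Baseline (Visit 2) and every scheduled 26 week clinic visit post-randomisation", and analysed "using a general linear model with effects for treatment, cluster, and baseline Qmax".

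Prostate volume is measured once before randomisation, at Visit 1b or from a historical TRUS (sections 7.1 and 7.2.2.2). PSA is measured once, at Visit 1a (section 7.3.4.2).

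**The concern.** A single questionnaire score, or a single void, measures a man's underlying severity with error. A second pre-randomisation reading, used as a covariate, can recover part of what the first one misses. Because it is fixed before allocation, it introduces no systematic bias into the treatment effect.

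If the earlier score carries information about Month 24 beyond the Visit 2 score, the planned model leaves the confidence interval wider, and the power lower, than the collected data allow. The same IPSS model is applied at every post-baseline visit and so also drives the step-down sequence in section 9.3.5.1. No sample size re-estimation is planned (section 9.2.3), which leaves covariate adjustment as one of the few ways to protect power.

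**Working it through.** **1. The plan's own figures.** Section 9.2.1 gives a difference of 1.8, SD 6 and 90% power; section 9.1 gives two-sided alpha 0.05.
- n per arm = 2(1.960 + 1.282)² × 6² / 1.8² = 233.5, so 234. Stated: 234.
- 234 / 0.80 = 292.5, so 293 per arm and 586 in total. Stated: 293 and 586.
- Power = Φ(d / (6√(2/234)) − 1.96). For d = 1.6, 1.8 and 2.0 this is 82.2%, 90.1% and 95.0%. Stated: 82%, 90% and 95%.

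The sample size section is therefore sound.

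**2. Formula for the gain.** Let a = corr(Visit 2, Month 24), b = corr(Visit 1a, Month 24) and c = corr(Visit 1a, Visit 2).
- Residual variance with one baseline: 1 − a².
- With two: 1 − (a² + b² − 2abc)/(1 − c²).
- The second covariate adds nothing when b = ac.

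The documents give none of a, b or c, so every value below is an assumption. SD 6 is taken as the residual SD of the planned one-baseline model.

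**3. Without the entry restriction.**
- a = b = c = 0.5: (1 − 0.3333)/(1 − 0.25) = 0.889, a cut of 11.1%.
- a = b = 0.5, c = 0.7: (1 − 0.15/0.51)/0.75 = 0.941, a cut of 5.9%.
- a = 0.5, b = 0.4, c = 0.7: (1 − 0.13/0.51)/0.75 = 0.993, a cut of 0.7%.
- a = 0.5, b = 0.35, c = 0.7: b = ac, so the cut is zero.

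**4. With Visit 1a restricted to IPSS 12 or more.** The entry rule narrows the spread of the Visit 1a score and so reduces what it can explain. These are simulations, assuming a screened population with mean 14-17 and SD 7.

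| Assumed a, b, c | Cut in residual variance | Power, 234 per arm, d = 1.8 |
|---|---|---|
| 0.3, 0.3, 0.3 | 2-3% | about 91% |
| 0.5, 0.5, 0.5 | 6-7% | about 92% |
| 0.5, 0.5, 0.7 | about 4% | about 91% |
| 0.5, 0.45, 0.7 | about 2% | about 90.5% |
| 0.5, 0.4, 0.7 | about 0.5% | about 90% |
| 0.5, 0.35, 0.7 | 0% | 90.1% |

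A second model gives cuts of 5-7%. It assumes stable severity, independent visit error and two-year drift, with the same entry rule and a change SD of 5.8 to 6.4, close to the plan's 6.

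**5. What a 7% cut is worth.**
- Power at d = 1.8: Φ(3.245/√0.93 − 1.96) = Φ(1.405) = 92.0%.
- Power at d = 1.6: from 82% to about 85%.
- Confidence interval width: 1 − √0.93 = 3.6% narrower.
- Equivalent sample: 234 × 0.93 = 217.6, so 218 per arm, a saving of 16 evaluable men per arm.

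**6. Qmax.** Equal correlations of 0.4 to 0.6 give cuts of 8-14% if entry limits are ignored. Inclusion criterion 6 keeps only screening values above 5 and up to 15 mL/sec. Applying that (screened mean 10-12, SD 4-5 assumed) brings the cut down to about 3-8%, and to about zero where b is close to ac.

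**The case against.** The strongest reply is that nothing here is wrong. Change adjusted for baseline score and cluster is a standard, valid model, and it is powered as stated. This stands in full.

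The gain may also be nil. Visit 1a falls about six weeks before Visit 2, with a placebo run-in between them that section 3.1 says is meant to reduce placebo response. Visit 1a may therefore say little about Month 24 that Visit 2 does not. This stands too, and is why the range starts at zero.

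Three practical points stand as well:
- Only IPSS and Qmax are entry-tested at screening. The earlier BHS, BII and PAS-SFI values are scheduled but not guaranteed, and a general linear model drops any man with a missing covariate.
- Under the Table 1 footnote, Visit 1b Qmax is repeated only when the Visit 1a value did not meet the entry criteria. A qualifying screening value therefore mixes first readings with readings kept because they passed.
- If SD 6 is read as the SD of raw change, the planned model already exceeds 90% power. In the stable-severity scenarios it has 91.3-94.3%, and the added term brings 1 to 2 points.

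What does not stand is that the matter can simply be left to the reporting and analysis plan. The protocol itself writes out the covariate list for the primary test. Section 9.3.7 does allow additions to be documented in that plan, which gives a route for the change.

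**Conclusion.** The point holds as a missed efficiency. On every eligible man there are two pre-randomisation IPSS values, and the fixed primary model uses one. Adding the other would cut residual variance by 0 to about 7%, with power going from 90% to about 90-92% at 234 per arm and a difference of 1.8. For Qmax the cut is 0 to about 8%. All of this rests on assumed correlations and assumed screened distributions.

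A reader might infer more in three ways, and the documents support none of them:
- **That the trial is underpowered or the primary analysis biased.** The stated sample size and power table reproduce, and the one-baseline model is valid.
- **That every continuous model discards data.** Prostate volume and PSA have a single scheduled pre-randomisation value, so nothing is lost there.
- **That a gain above 10% can be expected.** For IPSS that needs the entry restriction to be ignored, or a common correlation near 0.7 (10-12% even with the restriction). The latter treats scores two years apart as being as closely related as scores six weeks apart.

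**What to change.** Before unblinding, keep Visit 2 as the baseline for computing change and pre-specify the primary model as: change in IPSS = treatment + cluster + Visit 2 IPSS + Visit 1a IPSS. Do not average the two scores into a new baseline, since that would bring pre-run-in values into the change score.

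Optionally, do the same for Qmax (using the qualifying screening value, stated explicitly), for BHS and BII (Visit 1a) and for PAS-SFI (Visit 1b). State a simple rule for a missing earlier value, such as imputing the mean of that baseline covariate, so that no ITT subject is dropped.

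The cost is one added term and one degree of freedom per model, with no new data, visits or patients. The downside is that there may be no gain.
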